3.6 Administration of Study Medication

is confidential.

t is confidential.

4 Endpoints

4.1 Primary Endpoint

The primary endpoint of the study is the safety and tolerability of EQ001, as assessed by treatmentemergent adverse events (TEAEs), treatment-emergent serious adverse events (TESAEs), clinical laboratory values, vital signs, 12-lead electrocardiogram (ECG), and physical examinations.

4.2 Secondary Endpoints

The secondary endpoints of the study are:

 Pharmacokinetics of EQ001, as assessed by EQ001 serum concentrations at specified timepoints

4.3 Exploratory Endpoints

• For Type B cohort subjects: Change from baseline in the Short-Form 36 Health Survey (SF-36) and FACIT-F (Additional Concerns domain) total score to FU1 and FU2 and change from

baseline in the Lupus Quality of Life (QoL), patient global assessment, and physician global assessment (PGA) to FU2

5 Analysis Populations

5.1 Safety Population

The Safety Population consists of all subjects who receive any study drug. All safety data summaries will use this population.

5.2 PK Population

The PK Population consists of subjects in the Safety Population who have at least one measurable post-EQ001 exposure serum concentration.

5.4 Efficacy Population

The Efficacy Population consists of subjects in the Safety Population who have at least one posttreatment assessment for a marker of clinical activity. Note that for Type B subjects, only post-treatment within 14 weeks of last treatment will be considered for the purpose of defining the Efficacy Population.

6 General Considerations

6.1 General Methods

Statistical analysis of data from this study will be performed using SAS version 9.4 or higher.

Summaries of baseline characteristics (including demographics), safety, PD parameter receptor occupancy, and efficacy will be presented for each EQ001 dose level within each Type A cohorts and the Type B cohort as applicable. Additionally, data will also be summarized for all Type A subjects combined. A given dose may be studied in more than one cohort of Type A subjects and/or in Type B subjects. Selected safety summaries will also be produced that combine like doses across Type A and B cohorts.

Groups Presented for Baseline Characteristics, Safety, PD, and Efficacy Data Summaries

Type A Cohorts

- Dose 1
- Dose 2
- Dose 3
- Dose 4
- Dose 5
- All doses combined

Type B Cohort

Dose 1

Type A + Type B Cohort

Selected summaries that combine doses across Type A and B cohorts will be produced for the following: Adverse events by systemic organ class (SOC) and preferred terms, adverse events of special interest, serious adverse events, and adverse events resulting in study drug discontinuation. Like doses from Type A and Type B will be pooled, eg., Type A Dose 1.6 mg/kg combined with Type B Dose 1.6 mg/kg.

As the primary objective of this Phase 1b study is to characterize the safety and tolerability of EQ001, no formal statistical hypothesis testing will be performed. Confidence intervals (CIs) for selected clinical activity parameters may be presented for exploratory purposes only.

Most statistical summaries will be descriptive in nature. Unless otherwise indicated, continuous variables will be summarized using the number of observations (n), mean, standard deviation (SD), median, minimum, and maximum and categorical variables will be summarized using number of observations (n), frequency and percentages of subjects.

All dosed subjects will be included in subject data listings unless otherwise noted. If applicable, the relative day (i.e., relative to date of first dose of study treatment) of all complete dates will be presented in subject listings.

Data collected at unscheduled visits will also be included in the subject listings.

Adverse events, medical and surgical histories will be coded for summarization using the Medical Dictionary for Regulatory Activities (MedDRA[®] Version 23.1). Concomitant medications will be coded using the World Health Organization (WHO) Drug Dictionary Global B3 (March 2019 Version).

Summary will include data at all scheduled visits and at last post-baseline visit. All by visit summaries will use the electronic case report form (eCRF) collected nominal visit.

For UPCR, urine albumin creatinine ratio (UACR), eGFR, creatinine, urine protein, urine creatinine, urine albumin, and SLEDAI-2K, all nominal visits will be analyzed as collected in the eCRF except for unscheduled and early termination (ET)

t is confidential.

Page 34 of 55

Statistical Analysis Plan Sponsor: Equillium Inc.; Protocol No.: EQ001-19-002

6.4 Pooling of Centers

Data from all the sites will be pooled together for the analyses.

| is confidential. | | |
|----------------------|------------------|-------|
| | Page 35 o | of 55 |

is confidential.

7 Non-Efficacy Data Summaries

7.1 Subject Disposition

Subject disposition data will be summarized using the Safety Population. This summary will include the number and percent of subjects in each of the analysis populations (Safety, Efficacy, PK and PD), subjects completing treatment and study, and subjects discontinuing treatment and discontinuing the study by the primary reason for discontinuation. Study completion is defined by completion of the last scheduled study visit (i.e. The FU2 for Type A subjects and the FU4 visit for Type B subjects), even if some earlier visits were missed. Continuous summary statistics will be presented for follow-up duration, where the follow-up duration in weeks will be calculated as:

Follow-up duration (weeks) = (date of last contact – date of first dose of study drug + 1) / 7, rounded to 1 decimal place.

The number of subjects enrolled and by site, and the number and percent of subjects who failed screening, along with the reasons for screen failure will be presented for all subjects who signed informed consent. By-subject listings will also be created for disposition data.

7.3 Demographic and Baseline Characteristics

A summary of demographics and baseline characteristics will be presented using the Safety Population. The following variables will be summarized using continuous or categorical descriptive statistics as appropriate:

- Age (years)
- Sex
- Race
- Ethnicity
- Body Mass Index (kg/m²)
- Baseline renal function (eGFR) (mL/min/Specific Surface Area [SSA]; SSA=1.73 m²)
- Baseline 24-hour UPCR (mg/g) (for Type B only)
- Baseline spot UPCR (mg/g)
- Baseline 24-hour UACR (mg/g) (for Type B only)
- Baseline spot UACR (mg/g)
- Baseline complements (C3 and C4)
- Baseline serologic markers (anti-dsDNA)
- Baseline anti-C1q (for Type A only)
- Prior and current medications used for SLE including biologic therapies for SLE
- History of prior induction treatments (for Type B only)

A by-subject listing will also be created for demographics and baseline characteristics data.

7.4 Baseline Disease Characteristics

For Type A subjects, time from initial diagnosis of SLE to first dose date in years will be summarized for the Safety Population.

For Type B subjects, baseline disease characteristics include time from initial diagnosis of SLE to first dose date in years, time from first biopsy-proven diagnosis of lupus nephritis to first dose in months, time from most recent kidney biopsy date to first dose in months, and most recent kidney biopsy findings regarding presence of lupus nephritis for the Safety Population. Lupus nephritis ISN/RPS class(es) category will also be summarized. For top data summarization purposes, ISN/RPS category will be determined by the main classes a subject belongs to. For example, if a subject belongs to ISN/RPS class(es) classes III (A) and IV-S(A), category will be designated as III+IV. Simply put, category is determined by ignoring the additional information after the main class (ie the S and G and the (A) or (C). NIH activity index and chronicity index will be summarized using descriptive statistics. NIH activity index is recorded in the database as x/24, only x whole number will be used for summarization. x ranges from 0-24. Chronicity index is recorded as x/12 in the database, only x will be used for summarization, x ranges from 0-12.

Approximate time from diagnosis of SLE to first dose in years will be calculated as (year of first dose – year of diagnosis + 1). Time from first biopsy-proven diagnosis of lupus nephritis to first dose in Type B subjects in months will be calculated as (first dose date – date of biopsy-proven diagnosis) / 30.4375. Time from the most recent kidney biopsy date to first dose in Type B subjects in months will be calculated as (first dose in Type B subjects in months will be calculated as (first dose date – date of biopsy-proven diagnosis) / 30.4375. Time from the most recent kidney biopsy date to first dose in Type B subjects in months will be calculated as (first dose date – date of most recent kidney biopsy) / 30.4375. Months will be rounded to one decimal place.

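### SAP 7.4 adds 1 to a difference of calendar years, so every subject's time since SLE diagnosis is overstated by between 0 and 2 years

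*SAP*

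**What the plan says.** SAP 7.4 names an elapsed time as the quantity to be reported. For Type A: "For Type A subjects, time from initial diagnosis of SLE to first dose date in years will be summarized for the Safety Population". The entry for Type B is similar: "baseline disease characteristics include time from initial diagnosis of SLE to first dose date in years". It then gives one rule for computing it, under which the approximate interval "will be calculated as (year of first dose – year of diagnosis + 1").

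The other two intervals in that paragraph are plain date differences converted to months: "first dose date – date of biopsy-proven diagnosis) / 30.4375" for nephritis, and "first dose date – date of most recent kidney biopsy) / 30.4375" for the latest biopsy.

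The SAP does add 1 elsewhere, but on a scale of days. Follow-up duration in SAP 7.1 is ("date of last contact – date of first dose of study drug + 1) / 7", and exposure duration in SAP 10.1 follows the same pattern.

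Protocol 13.5 also lists time since SLE diagnosis among the history data, measured there to Screening.

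**The concern.** Adding 1 is the usual way to count days inclusively, where it costs one day. Here the unit is the year, so the same step adds a whole year. The result is labelled as an elapsed time but is shifted in one direction for everyone.

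What is at stake is the description of who was studied. Time since SLE diagnosis is the only variable that SAP 7.4 lists for Type A. A subject diagnosed shortly before dosing cannot appear as such, because the smallest possible value is 1 year.

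**Working it through.** **Inputs.** The formula and the comparison formulas come from SAP 7.1 and 7.4. The documents give no diagnosis or dosing dates and no stated result to reproduce, so the dates below are illustrations.

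**Algebra.** Let first dose fall at Y1 + f1 and diagnosis at Y0 + f0, where Y is the calendar year and f the fraction of it elapsed (0 ≤ f < 1).

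- True duration = Y1 − Y0 + f1 − f0
- SAP value = Y1 − Y0 + 1
- Error = 1 + f0 − f1

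Since f0 − f1 lies strictly between −1 and +1, the error lies strictly between 0 and 2 years. Put another way, two calendar years alone place the true duration between Y1 − Y0 − 1 and Y1 − Y0 + 1. The SAP assigns everyone the upper limit; the midpoint is Y1 − Y0.

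**Dated examples** (true duration = days / 365.25):

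| Diagnosis | First dose | True | SAP value | Error | Error without the 1 |
|---|---|---|---|---|---|
| 31 Dec 2020 | 1 Jan 2021 | 0.003 | 2 | +1.997 | +0.997 |
| 31 Dec 2015 | 1 Jan 2021 | 5.005 | 7 | +1.995 | +0.995 |
| 1 Jul 2015 | 1 Jul 2021 | 6.001 | 7 | +0.999 | −0.001 |
| 1 Jan 2015 | 31 Dec 2021 | 6.998 | 7 | +0.002 | −0.998 |

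The last three subjects all show 7 years.

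**Mean error** = 1 + E(f0) − E(f1).

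- Dosing spread evenly over the year: simulating 1,000,000 date pairs gave a mean error of 1.00 year for uniform durations of 0 to 20 years and for exponential durations with means of 0.5, 1, 2 and 8 years. Without the 1 it was 0.00 in each case.
- Dosing concentrated, with exponential durations of mean 8 years: 1.47 if all in January, 1.25 if all in the first half-year, 0.75 if all in the second half, 0.55 if all in December. A hand check with E(f0) near 0.5 agrees: January 1 + 0.5 − 1/24 = 1.46; December 1 + 0.5 − 23/24 = 0.54.
- Subjects diagnosed in the calendar year of dosing: about 0.7 year on average (0.67 to 0.76 over the distributions tried).

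**Chance variation.** If f0 and f1 are independent and uniform, the SD of one subject's error is √(1/12 + 1/12) = 0.41 year. The standard error of the mean error is then 0.41/√30 = 0.07 for 30 Type A subjects and 0.41/√20 = 0.09 for 20 Type B subjects. The shift would not average out.

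**Comparison with the day-scale use.** In SAP 7.1 the added 1 is divided by 7 and contributes 1/7 week. In SAP 7.4 it is not divided and contributes a full year.

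**The case against.** The SAP calls the value approximate and prints the formula, so a reader can subtract 1. That is fair as to whole-year resolution, which may be all that the data allow. It does not cover a shift in one direction, because the same two years give a centred value without the 1. Nor is this rounding up: a subject diagnosed one day before dosing can be given 2 years.

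A reader might infer more than the documents support:

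- *Each subject is wrong by exactly one year.* One year is a mean, and it depends on where dosing and diagnosis fall in the calendar year. With sequential Type A cohorts and up to about 20 Type B subjects, an even spread cannot be taken for granted.
- *The added 1 makes SLE and nephritis durations non-comparable.* No such comparison is planned, and one is in whole years while the other is in months to one decimal. A subject with both diagnosed three months before dosing would show 1 or 2 years against 3.0 months now, and 0 or 1 year against 3.0 months after the fix.
- *Both cohort types lose one of very few disease descriptors.* In Type B, SAP 7.4 also gives nephritis and biopsy timing, biopsy findings, ISN/RPS class, and activity and chronicity indices. SAP 7.3 adds eGFR, spot UPCR, complement and anti-dsDNA for both types.
- *Results on safety or activity are affected.* No visible endpoint, model, eligibility rule or dose decision uses SLE duration, and SAP 6.1 plans no formal testing.

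**Conclusion.** The formula is wrong as written for the quantity it is meant to give. That every subject is overstated, by more than 0 and less than 2 years, follows from the algebra and needs no assumption. The mean of about one year assumes that dosing and diagnosis dates have the same average position in the calendar year. The range of about 0.55 to 1.47 covers dosing wholly in December or wholly in January, under exponential durations with a mean of 8 years.

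The consequence is small: one descriptive baseline variable is shifted upward and cannot fall below 1 year. SAP 2.2 reports that a Type A analysis has been done, but the documents do not say whether it used this formula, so it cannot be claimed that a wrong figure has already been reported.

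**What to change.** Delete the added 1, so that the rule becomes year of first dose minus year of diagnosis. This removes the built-in shift but leaves an individual error between −1 and +1 year. If dosing were concentrated in one month, a smaller mean error would remain: 0.55 − 1 = −0.45 year for December, 1.47 − 1 = +0.47 for January.

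If full diagnosis dates were collected, use (first dose date − diagnosis date) / 365.25 instead. The visible text does not show whether they were. Choose one rule for the whole variable, so that exact and whole-year values are not mixed.

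Apply the same formula to Type A and Type B in the final analysis, and footnote any Type A figure already produced with the added 1. The cost is one SAP edit, one line of code and, if the Type A analysis used the formula, a rerun of that table. No new data and no change to any endpoint are needed.

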7.5 Medical and Surgical History

Medical and surgical history will be coded using MedDRA version 23.1. The percentage of subjects with a medical history event will be summarized descriptively using the Safety Population. The table will be sorted in descending frequency of MedDRA system organ classes (SOC) and within each SOC by descending frequency of preferred terms (PT) in the Total column (all subjects pooled). A by-subject listing will also be created.

7.6 Medications

All medications will be coded using WHO Drug Dictionary (WHODrug Global B3 September 2020 version). Medications will be summarized by Anatomic Therapeutic Class (ATC) level 2 terms (ATC2) and ATC level 4 terms (ATC4) using the Safety Population. Subjects will be counted only once for each ATC2 term in the event that they have multiple records of the same ATC level in the database. The tables will be sorted in the descending order of frequency ATC2 terms and within each ATC2, descending order of frequency of ATC4 in the Total column (all subjects pooled). By-subject listings will also be created.

7.6.1 Prior Medications

Prior medications are defined as those medications with a start date prior to the first dose date of any study drug. Prior medications will be summarized in a table and presented in a by-subject listing.

is confidential.

7.6.2 Concomitant Medications

Concomitant medications are defined as any medications taken on or after the date of first dose of any study drug, including any medications that were started before the first dose date of any study drug and are ongoing. Concomitant medications will be summarized descriptively and presented in a by-subject listing.

Medications can be both prior and concomitant depending on the start and stop date as related to the first dose date of any study drug.

7.6.3 Induction Treatments

Summary of induction treatments is provided for Type B subjects only using the Safety Population. Time from last induction regimen to first dose (months) and time from last best response to first dose (months) will be summarized as continuous variables. Time from last induction treatment start date to first dose is calculated as (first dose date – start date of last induction treatment) / 30.4375, rounded to one decimal place. Time from last response is calculated as (first dose to first dose to first dose is calculated as (first dose date – end date of the last best response) / 30.4375, rounded to one decimal place. Best response and the last induction regimen will be summarized as categorical variables.

Complete response or partial response are considered as best response for the calculation of time from last best response to first dose. Complete Response > Partial Response > No Response > Ongoing > Unknown where '>' symbol indicates 'better than' and 'Ongoing' indicates that the treatment is ongoing.

7.6.4 Systemic Steroid Use

All systemic steroid use will be summarized by ATC2 and ATC4 using the Safety Population. Subjects will be counted only once for each ATC2 term in the event that they have multiple records of the same ATC level in the database. The tables will be sorted in the descending order of frequency ATC2 terms and within each ATC2, descending order of frequency of ATC4 in the Total column (all subjects pooled). By-subject listings will also be created.

7.6.5 Systemic Lupus Erythematosus Treatments

The most recent use of prior systemic lupus erythematosus treatments will be summarized by drug/drug class as collected in the CRF and by use (never used, discontinued >6 months ago, discontinued <= 6 months ago, ongoing, unknown) using the Safety Population. By-subject listings will also be created.

8 Efficacy

Unless otherwise specified, all efficacy endpoints (clinical activity endpoints) will be summarized using the Efficacy Population for the EQ001 treatment group from each Cohort.

Efficacy data will be analyzed based on the scheduled visits. For sensitivity analysis of Type B subjects, data collected more than 56 days after the last treatment date, or after a subject received new immunosuppressive or other treatments for LN, or after subject had an increase in glucocorticoids will be considered as missing. Details will be described in Section 8.1.

This document is confidential.

For both Type A and Type B Cohort subjects, the fold change from baseline in spot UPCR will be descriptively summarized using geometric statistics (geometric mean, geometric CV etc.). The proportion of subjects with a > 30% and > 50% decline in spot UPCR and those with a spot UPCR < 500 mg/g by visit will be described, along with their 2-sided exact Clopper-Pearson 95% CIs specifically provided for FU1 for Type A subjects and FU2 for Type B subjects.

In addition, an exploratory analysis of spot UPCR will be performed for Type A cohorts. In this analysis, two-sided p-value to compare values from FU1 and baseline will be obtained by testing LS mean associated with each dose resulting by fitting an ANCOVA model equals to 0. ANCOVA model will be fitted to the log-transformed fold change data with EQ001 dose level as a factor and log-transformed baseline spot UPCR as a covariate for Type A cohorts.

8.1.2 Change from Baseline to FU1 and FU2 in Serologic Markers (C3, C4, and anti-dsDNA)

This endpoint pertains to both Type A and Type B Cohort subjects.

The mean change from baseline in C3, C4, and anti-dsDNA to FU1 (Type A Cohorts [exploratory endpoint]) and FU2 (Type B [secondary endpoint]) will be summarized, along with their 2-sided 95% CI for the change. For data summarization purposes, if a value is recorded as <x or <=x, the value is considered as x/2. If a value is recorded as >x or >=x, the value is considered as x. For Type A, the 2-sided 95% CI will be presented by fitting an ANCOVA model, that is, an ANCOVA model on the changes in C3 and C4, from baseline to FU1 with EQ001 dose as a factor and baseline value as a covariate will be fitted. Baseline adjusted LS mean changes from each group will also be reported.

Serologic markers are collected from central and local laboratories for Type B cohort. Same tests with both central and local version will be combined and analyzed, using descriptive summary statistics by assessment visit. For site 8xx subjects, only local laboratory data (may come from different local laboratories) will be used for analysis; for non-site 8xx subjects, only central laboratory data will be used for analysis.

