8 INVESTIGATIONAL PLAN

8.1 Overall Study Design and Plan

This is a Phase 1b, multiple ascending-dose study to evaluate the safety, tolerability, PK, clinical activity of EQ001, a humanized IgG1 mAb that selectively targets CD6 on T_{eff} cells, in subjects with SLE.

Approximately 30 subjects with active or inactive SLE who do not have apLN are anticipated to be studied in dose escalation cohorts of 6 subjects each in Type A Cohorts. Up to approximately 20 subjects with apLN are anticipated to be studied in a Type B Cohort. Additional subjects may be added at the maximum-tolerated dose (MTD) cohort and/or to an additional cohort at an intermediate or lower dose in Type A. The exact numbers of each type of cohort will be determined by emerging data during the study.

To qualify for enrollment in the study, all subjects must have a diagnosis of SLE. Additionally, to qualify for enrollment in a Type B Cohort, subjects must have apLN, defined as proliferative LN (International Society of Nephrology [ISN]/Renal Pathology Society [RPS] Class III or IV with or without Class V) diagnosed by renal biopsy within 12 months prior to Day 1 or during Screening, and previous evidence of serologic and clinical disease activity. Type B Cohort subjects may require induction treatment for apLN for newly diagnosed disease or relapsing/flaring disease or need additional treatment for incomplete responders. Restricted SLE treatments (e.g., immunosuppressive medications and antimalarials) are required to be stable and/or washed out Subjects in the Type B Cohort may have glucocorticoids administered and tapered

Subjects in the Type B Cohort may have glucocorticoids administered to the protocol steroid taper schedule unless a safety concern (including concern related to insufficient response) necessitates departures from the schedule. Such planned departures must be discussed with the Medical Monitor, preferably in advance of the change in medication.

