8.1.1 Type A

Type A will utilize a cohort dose escalation design. If < 2 of the 6 evaluable subjects in a Type A dose-escalation cohort experience a dose-limiting toxicity (DLT) during the DLT evaluation period (Days 1-29), then escalation may occur to the next higher dose level. If 2 or more of the 6 initial subjects in a Type A dose-escalation cohort experience a DLT, then no further dose escalation will occur. That dose will then be considered to have exceeded the MTD and the next-lower dose may be declared the MTD. Once a dose has been determined to have exceeded the MTD, the Data Review Committee (DRC) may recommend continuation of the study (with or without modification) and may expand enrollment to evaluate additional subjects at the MTD and/or an additional cohort at an intermediate or lower dose to better define the MTD.

[figure not shown]
Type A Cohort enrollment will proceed in a sequential manner to evaluate escalating dose levels of EQ001. The first dose level to be studied, Dose Level 1, will be 0.4 mg/kg and the maximum

Equillium, Inc.	Clinical Study Protocol No. EQ001-19-002	Page 39 of 110
Equillium, Inc.	Clinical Study Protocol No. EQ001-19-002	Page 39 of 110

dose level to be studied will be 3.2 mg/kg. Intermediate dose levels of 0.8, 1.6, and 2.4 mg/kg are planned, but other intermediate doses may be chosen based on emerging PK, PD, and safety data. Subjects in Type A Cohorts will receive a total of 2 doses, 2 weeks apart.

The MTD determination will be made based only on Type A Cohorts. Dose escalation is allowed to proceed if no predefined stopping criteria are met and the DRC recommends that it is safe to proceed.

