8.4 Rationale for Study Design

The open-label study design will ensure subject safety by allowing frequent ongoing assessment of safety by the Sponsor, investigators, and the DRC. All subjects will receive EQ001. The dose levels selected (from 0.4 to 3.2 mg/kg) will allow an assessment of the full dose-response curve of EQ001. Dose escalation will occur by cohort following review of data by the DRC to allow emerging safety, PK, and other data to inform dose-escalation decisions based on pre-defined DLT criteria and stopping rules.

The Type A Cohort subjects will receive 2 doses of study drug, which are expected to have pharmacodynamic effects for approximately 4 weeks. The multiple ascending dose data from Type A Cohorts is expected to provide sufficient safety and pharmacokinetic data to allow the study of a dose (1.6 mg/kg) determined not to exceed the MTD in the apLN population (Type B Cohort subjects) over a longer duration. Type B Cohort subjects will receive 13 doses over 24 weeks as prolonged treatment may be needed for subjects with chronic disease. This is reflective of lupus nephritis induction treatments, which generally require at least 6 months of treatment as noted in the Kidney Disease Improving Global Outcomes (KDIGO) glomerulonephritis guidelines (https://kdigo.org/guidelines/gn/). Prolonged treatment will also enable a better understanding of the exposure-response relationship, long-term safety, dose selection, and the effect size.

This design feature is intended to minimize risk to subjects and to allow exploration of a safe range of doses over relatively short treatment duration as well as to explore doses associated with PD and clinical activity.

8.4.1 Rationale for Evaluating EQ001 for the Treatment of Patients with Systemic Lupus Erythematosus with or without Active Proliferative Lupus Nephritis

Current treatment for Class III and IV LN are non-targeted immunosuppressive medications: cyclophosphamide and/or mycophenolate with glucocorticoids

For patients who do not achieve remission with these treatments or who are unable to tolerate them, there is no standardized approach to management because there is a general lack of evidence-basis

This study will enroll subjects with biopsy-proven active proliferative Class III or IV (with or without Class V) LN who have proteinuria (> 1000 mg/g) and evidence of serologic activity who require induction treatment for apLN for newly diagnosed disease or

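### Protocol 8.4 says the Type A doses allow the full dose-response curve to be assessed, but no Type A analysis in the public SAP compares or models response across doses

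*SAP*

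**What the plan says.** **Design rationale.** Protocol 8.4 says that the selected doses, 0.4 to 3.2 mg/kg, "will allow an assessment of the full dose-response curve of EQ001". Protocol 8.1 plans for this part: "Approximately 30 subjects with active or inactive SLE who do not have apLN", "anticipated to be studied in dose escalation cohorts of 6 subjects each in Type A Cohorts". Protocol 8.1.1 sets the lowest and highest doses and adds: "Intermediate dose levels of 0.8, 1.6, and 2.4 mg/kg are planned". That makes five doses, and every subject receives EQ001.

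**Spot UPCR, Type A (SAP 8.1.1).** The exploratory model is described as follows: "ANCOVA model will be fitted to the log-transformed fold change data with EQ001 dose level as a factor", with log baseline as covariate. A "two-sided p-value to compare values from FU1 and baseline will be obtained by testing LS mean associated with each dose", the null value being zero.

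**C3 and C4, Type A (SAP 8.1.2).** The plan is "an ANCOVA model on the changes in C3 and C4, from baseline to FU1 with EQ001 dose as a factor", again with baseline as covariate. Adjusted mean changes and 95% CIs are reported by dose.

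**Everything else visible for Type A** is descriptive. Laboratory values, including lymphocyte counts, are summarised by visit, CTCAE grade, shift table and box plot (SAP 10.4). Serum concentrations are summarised by visit and group (SAP 9.1). Efficacy is also summarised with all Type A doses combined (SAP 6.1; Protocol 13.9). SAP 6.1 rules out formal hypothesis testing and allows exploratory confidence intervals.

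**The concern.** A dose-response statement is a statement about differences between doses. The visible models give five changes from baseline, and for spot UPCR the null hypothesis is that a given dose's mean change is zero. In an open-label study without an untreated group, that change mixes drug effect with regression to the mean and the passage of time. It can be non-zero at every dose when dose does not matter. Pooling all doses averages over dose, so it does not help.

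A contrast between doses removes whatever before-after shift the cohorts share, and it bears directly on the rationale in Protocol 8.4. Protocol 8.4.1 also says that studying each dose first in Type A supports optimised dose selection for the apLN population. The same question arises for safety. Protocol 8.3 names lymphopenia as a potential drug reaction, and Protocol 8.4.2 gives lymphocyte risk as a reason for the low starting dose. Yet no visible analysis estimates whether lymphocyte loss rises with dose.

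There is also no zero dose. Any curve is therefore relative to 0.4 mg/kg, and a full curve is more than the design can give.

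**Working it through.** **Inputs from the documents.** Five doses: 0.4, 0.8, 1.6, 2.4 and 3.2 mg/kg, with 6 subjects each. The planned total reproduces: 5 × 6 = 30. The documents give no power, alpha, residual SD or expected effect.

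**Assumptions.** Residual SD = s (all results are in units of s), baseline balanced across doses, two-sided 5%, and exactly 6 evaluable subjects per dose. The true difference between lowest and highest dose, D, runs from 0.5s to 2s and is linear in log dose.

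**1. What the planned per-dose results deliver**
- Residual df = 30 − 5 − 1 = 24.
- SE of one adjusted mean = s/√6 = 0.408s. The 95% half-width is 2.064 × 0.408s = 0.84s.
- Using only that dose's own 6 subjects (5 df), the half-width would be 1.05s. The model does borrow variance across doses.
- Flat response, change of 1s at every dose: noncentrality = √6 = 2.45, and power per test is 65%. Expected number significant = 5 × 0.652 = 3.3 of 5, with a true slope of zero.

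**2. What a slope in log dose would deliver**
- log2 doses: −1.32, −0.32, 0.68, 1.26, 1.68; mean 0.395.
- Sum of squared deviations = 2.948 + 0.514 + 0.080 + 0.753 + 1.646 = 5.94. Sxx = 6 × 5.94 = 35.65.
- SE per doubling = s/√35.65 = 0.1675s.
- From 0.4 to 3.2 mg/kg is 8-fold, or 3 doublings: SE = 3 × 0.1675s = 0.502s. Half-width (24 df) = 2.064 × 0.502s = 1.04s.

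**3. Benchmark: highest versus lowest dose only** (not planned either)
- SE = s√(2/6) = 0.577s; half-width 1.19s.
- Variance ratio = (0.577/0.502)² = 1.32. The slope is worth about 32% more subjects than this two-dose comparison.

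**4. Power** (noncentral t or F; shown only to convey precision)

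| D | slope in log dose | highest v lowest | 4-df test of any dose difference |
|---|---|---|---|
| 0.5s | 16% | 13% | 10% |
| 1.0s | 48% | 38% | 27% |
| 1.5s | 82% | 70% | 56% |
| 2.0s | 97% | 91% | 84% |

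Scoring on the mg/kg scale hardly changes this. Sxx = 31.49, the SE over the range is 2.8 × 0.178s = 0.499s, and for a response linear in dose the power of the slope is 16%, 49%, 82% and 97% for the same four values of D.

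**The case against.** **The remedy comes late.** SAP 2.2 says that Type A enrolment is complete, the database was frozen and an analysis was done. The Type B dose has already been chosen, partly on Type A results (Protocol 8.4.2). A slope added now is chosen after open-label data were seen. This stands: the slope must be labelled post hoc and cannot become the main Type A result.

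**Dose-response is one sentence, not an objective.** The visible objectives and endpoints do not include it, and Type A clinical activity is exploratory. The formal dose question in Type A is the MTD, which the DLT rule answers. This stands too. A reader might infer that Type A cannot answer its dose question without a trend; the documents do not support that.

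**The analysis may exist out of sight.** SAP 8.1.7 and 9.2 are absent from the public text, and receptor occupancy is summarised by dose (SAP 6.1). A reader might infer that dose-response is never estimated. That cannot be verified, so the point covers visible text only.

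**Dose as a factor imposes no shape, and five adjusted means do describe response by dose.** True, and a reason to keep them. It is also wrong to infer that the models look only within each group of 6, because residual variance and baseline slope are pooled over about 30 subjects. Still, five means without a contrast leave the cross-dose comparison to the eye.

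**A slope is confounded too.** Cohorts were sequential and not randomised, with mixed active and inactive SLE, so calendar drift and case mix can produce or hide a trend. This stands as a limitation to report. Spot UPCR may also have little room to fall, since Type A excludes a history of apLN and sets no proteinuria threshold.

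**Conclusion.** The mismatch is real. Protocol 8.4 offers assessment of the full dose-response curve as a rationale, and no visible Type A analysis compares or models response across doses. The planned per-dose tests cannot fill the gap: under a flat response of 1 residual SD, about 3.3 of the 5 would be significant.

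The consequence is modest. It does not touch the primary safety objective or the MTD rule. Nor would a slope settle the question: the SE over the full range is about 0.50 residual SD, and power is 48% for a true difference of 1 SD. The gain is an estimate with an interval where the visible plan has none. These figures assume 6 evaluable subjects per dose, balanced baselines, and an SD and effect size that the documents do not give. This is a cheap improvement, not a flaw that invalidates the plan.

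**What to change.** 1. In the final analysis, add to the existing Type A ANCOVAs for spot UPCR, C3 and C4 an exploratory linear contrast in log dose, reported as a slope per doubling with 95% CI. Keep the per-dose adjusted means beside it.
2. Fit one further model of the same form for change in absolute lymphocyte count. No lymphocyte ANCOVA is visible, so this is a new model and not just a contrast.
3. Present the slope as estimation. That fits SAP 6.1, which allows exploratory intervals, better than the p-values planned in SAP 8.1.1 do.
4. Reword Protocol 8.4 to claim a dose trend over 0.4 to 3.2 mg/kg, without a zero dose. If a dose- or exposure-response analysis sits in unpublished SAP text, refer to it there.

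**Cost.** One contrast in each of three models already planned, one extra model, and one sentence of protocol text.

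**Limits to state with the result.** The slope is post hoc. Sequential, non-randomised cohorts leave calendar drift and case-mix confounding. A linear trend can miss a plateau. Precision is modest.
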